Abbreviations: TMS: transcranial magnetic stimulation EEG: electroencephalography EMG: electromyography PNS: peripheral nerve stimulation PCMS: paired corticospinal-motoneuronal stimulation ISI: inter-stimulus interval TST: triple stimulation technique RMT: resting motor threshold M-max: intensity needed to elicit a maximal muscle response using PNS or TMS FDI: left first dorsal interosseous MEP: motor evoked potential

4 Design and Methodology

Provide information regarding study design or data collection methodologies. Details regarding protocol specific research procedures will be discussed in a later section.

To input text, click in the light grey area below.

For all experiments, single-pulse TMS will not be applied at a rate that exceeds 0.5 Hz. That is, at least 2 seconds will elapse between individual single TMS pulses.

Experiment 1

Design: within-subjects, single-group Population: healthy adults (≥ 18 years old) Conditions:

- 1. TMS during brain states reflecting strong corticospinal recruitment
- 2. TMS during brain states reflecting weak corticospinal recruitment
- 3. TMS may also be applied during random brain states
 - a. The order of conditions will be randomized

Session frequency: Up to 2 sessions for <= 6 hours. Each session will involve the same experimental procedures (see below). In the event of technical difficulties, a third session may be performed, during which any combination of the procedures described below may be applied. At least 24 hours will elapse between sessions. Methodology:

EEG recordings: EEG will be recorded while participants rest quietly with their eyes open and during stimulation procedures. 64 EEG electrodes will be secured to the scalp using a swim-like cap and electrode gel.

EMG recordings: EMG will be recorded from a maximum of 5 hand and wrist muscles while participants rest quietly and during stimulation procedures (see below, *Real-time brain state-dependent TMS*). EMG will be recorded from <= 8 hand and wrist muscles.

Brain state discovery: <= 600 single TMS pulses will be applied to the scalp at <= 120% of scalp RMT during EEG and EMG recordings. These data will be used to identify brain states reflecting strong versus weak corticospinal tract recruitment using machine learning.

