Real-time EEG analysis: The EEG system will stream data to a dedicated computer. This computer will analyze the data in real time to identify brain states associated with strong or weak corticospinal tract recruitment (see above), or a random mixture of the two.

Real-time brain state dependent TMS: The real-time EEG analysis algorithm will trigger delivery of a single TMS pulse when it identifies brain states predicted to reflect strong, weak, and/or random corticospinal tract

recruitment. <= 450 single TMS pulses at <=120% RMT during strong, weak and/or random brain states may be delivered.

Experiment 2

Design: within-subjects, single-group Population: healthy adults (≥ 18 years old) Conditions:

- 4. Triple stimulation technique (TST) assessment during brain states reflecting strong corticospinal recruitment
- 5. TST assessment during brain states reflecting weak corticospinal recruitment
- 6. TST assessment during random brain states
 - a. The order of conditions will be randomized

Session frequency: Up to 2 sessions for <= 6 hours. Each session will involve the same experimental procedures (see below). In the event of technical difficulties, a third session may be performed, during which any combination of the procedures described below may be applied. At least 24 hours will elapse between sessions. Methodology:

EEG recordings: EEG will be recorded while participants rest quietly with their eyes open and during stimulation procedures. 64 EEG electrodes will be secured to the scalp using a swim-like cap and electrode gel.

EMG recordings: EMG will be recorded while participants rest quietly and during stimulation procedures (see below, *Calculation of ISIs for TST assessment* and *TST assessment*). EMG will be recorded from a maximum of 5 hand and wrist muscles.

Brain state discovery: <= 600 single TMS pulses will be applied to the scalp at <= 120% of scalp RMT during EEG recordings. These data will be used to identify brain states reflecting strong versus weak corticospinal tract recruitment using machine learning.

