Real-time EEG analysis: The EEG system will stream data in real-time to a dedicated computer. This computer will analyze the data in real time to identify brain states associated with strong or weak corticospinal tract recruitment (see above), or a random mixture of the two. When desired states are identified, either a single TMS pulse (see *Evaluation of state-targeting* accuracy) or the TST (see *TST assessment*) will be triggered. *Evaluation of state-targeting accuracy:* <= 150 single TMS pulses will be applied to the scalp at <= 120% of scalp RMT during EEG recordings.

Calculation of ISIs for TST assessment: The following stimulation procedures will be performed to calculate the ISIs for TST assessment.

- 1. <= 25 Single-pulse TMS to the scalp at <= 120% of scalp RMT
- 2. <= 25 Single-pulse PNS to the left wrist at <= 120% of M-max
- 3. <= 25 Single-pulse PNS to the left Erb's point at <= 120% of M-max

TST assessment: The TST will be applied according to an established protocol (Magistris et al. 1998) using consecutive application of TMS (<= 120% of scalp RMT), PNS at the left wrist (<= 120% of M-max), and PNS at the left Erb's point (<= 120% of M-max). The delays between each stimulus will be individualized based on each participants central and peripheral conduction times (see *Calculation of ISIs for TST assessment*). The TMS portion of the TST will be timed to occur during brain states reflecting strong corticospinal tract recruitment, weak corticospinal tract recruitment, or random brain states, using real-time EEG analysis. <= 50 TST applications will be performed per brain state condition.

Experiment 3

Design: within-subjects, single group Population: healthy adults (≥ 18 years old)

Conditions: At least 24 hours will elapse between sessions.

- 1. Active PCMS delivered during brain states reflecting strong corticospinal recruitment
- 2. Active PCMS delivered during brain states reflecting weak corticospinal recruitment
- 3. Active PCMS delivered during random brain states

- 4. Control PCMS delivered during brain states reflecting strong corticospinal recruitment
 - a. The order of conditions will be counterbalanced
 - b. Participants may complete one, two, three or four of the conditions

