Spinal excitability measurements: <= 25 single PNS pulses to the left wrist at <= 120% of M-max. Measurements will be taken immediately before PCMS and at 0, 20 and 40 minutes after PCMS.

Voluntary motor output measurements: <= 5 maximum voluntary contractions of the FDI, each lasting <= 5 seconds. Measurements will be taken immediately before PCMS and at 0, 20 and 40 minutes after PCMS. Manual dexterity measurements. <= 5 attempts of the 9-hole peg test. Measurements will be taken immediately before PCMS and at 0, 20 and 40 minutes after PCMS.

5 Data Analysis

Describe the data analysis plan, including any statistical procedures or power analysis. To input text, click in the light grey area below.

Experiment 1:

- 1. Primary outcome: Amplitude of MEPs evoked during brain states reflecting strong, weak, and/or random corticospinal tract recruitment
 - a. This outcome will be evaluated using linear-mixed effects models (fixed effect of state, random effect of subject) with alpha equal to 0.05.

Experiment 2:

- 1. Primary outcome: amplitude of FDI muscle response after TST application during brain states reflecting strong, weak, and random corticospinal tract recruitment.
- 2. Secondary outcome: area under the curve of FDI muscle response after TST application during brain states reflecting strong, weak, and random corticospinal tract recruitment.
 - a. Both outcomes will be evaluated using linear mixed-effects models (fixed effect of state, random intercept of subject) with alpha equal to 0.05.

Experiment 3:

- 1. Primary outcomes: Maximum FDI force output, FDI activation (calculated using the root-mean-square of EMG signals obtained during FDI contractions)
- 2. Secondary outcome: Number of pegs placed per attempt at the 9-hole Pegboard test.
- 3. Exploratory outcomes: Amplitudes of MEPs produced by scalp TMS, amplitudes and persistence of Fwaves evoked by wrist PNS
 - All outcomes will be evaluated before and after PCMS. Outcomes will be analyzed using linearmixed effects models (fixed effects of condition and time point, random intercept of subject).
 Main effects will be evaluated using likelihood ratio tests, and p-values from post-hoc contrasts will be corrected for multiple comparisons. Alpha will be equal to 0.05.

STUDY ELEMENT IDENTIFICATION

6 Study Elements

Click on the check box (or double click and type an "X" if using Google Docs) each procedure included in your study.

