- The real-time EEG algorithm will be used to deliver <= 150 single TMS pulses during brain states associated with strong corticospinal recruitment, <= 150 single TMS pulses during brain states associated with weak corticospinal recruitment, and/or <=150 single TMS pulses during randomly selected brain states, for a total of <= 450 single TMS pulses. During this time, participants will rest quietly with their eyes open (Zrenner et al. 2018; [name] et al. 2020).

- We may also record EEG signals at any time point during testing while participants rest quietly with their eyes open.
- The EEG cap and EMG electrodes will be removed and participants will leave the laboratory.
- If participants are asked to complete two sessions, the same experimental procedures described above may be used during the second session. The second session may be used to evaluate between-day reliability of the measurements made during the first session. At least 24 hours will elapse between sessions.

Experiment 2:

- The participant and research team member will review and discuss the informed consent document.
- Eligibility will be formally determined by the research team member by reviewing a list of the inclusion and exclusion criteria with the participant (see attachments).
- Participants will complete a short demographics survey.
- The EEG cap containing will be positioned on the participants head according to the 10-20 International EEG system (Seeck et al. 2017). The scalp beneath each electrode may be cleaned with alcohol, and an electrolytic gel will be applied beneath each electrode. Afterwards, the scalp may be lightly abraded using a blunt needle.
- The skin on the left hand, left wrist, and left Erb's point will be cleaned using isopropyl alcohol. EMG electrodes will be attached to a maximum of 5 hand and wrist muscles using medical grade adhesive. PNS electrodes will be attached to the left wrist and left Erb's point using medical grade adhesive. A ground electrode will attached to the dorsum of the hand in the same manner.
- The scalp TMS hotspot will be determined as the site of the scalp producing the most reliable focal muscle twitch within the left FDI. The scalp RMT will be determined using an automatic threshold tracking tool (Awiszus and Borckhardt 2011) as the minimum stimulation intensity needed to elicit an MEP of 50 microvolts in peak-to-peak amplitude in response to 50% of stimuli. EMG and EEG signals may be recorded for offline quality control analysis.

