- The TST will be applied during brain states reflecting strong corticospinal recruitment, brain states reflecting weak corticospinal recruitment, and randomly selected brain states according to an established procedure (Magistris et al. 1998), with details below. EMG data will be recorded and processed offline to calculate the primary and secondary outcomes. EEG data will be recorded and processed offline to ensure accurate state identification as a quality control procedure (Zrenner et al. 2018; [name] et al. 2020).
 - TMS will be timed using the real-time EEG analysis algorithm
 - After an interstimulus interval equal to delay 1, Wrist PNS will be applied.
 - After an interstimulus interval equal to delay 2, Erb's point PNS will be applied.
- The EEG cap, EMG electrodes, and PNS electrodes will be removed and participants will leave the laboratory.
- If participants are asked to complete two sessions, the same experimental procedures described above may be used during the second session. The second session may be used to evaluate between-day reliability of the measurements made during the first session. At least 24 hours will elapse between sessions.

Experiment 3

Days 1-4 (at least 24 hours will elapse between sessions)

- The participant and research team member will review and discuss the informed consent document.
- Eligibility will be formally determined by the research team member by reviewing a list of the inclusion and exclusion criteria verbally with the participant (see attachments).
- Participants will complete a short demographics survey.
- The skin on the left hand and wrist will be cleaned using isopropyl alcohol. EMG electrodes will be attached to a maximum of 5 hand and wrist muscles using medical grade adhesive. PNS electrodes will be attached to the left wrist using medical grade adhesive. A ground electrode will also attached to the dorsum of the hand in the same manner.
- The scalp TMS hotspot will be determined as the site of the scalp producing the most reliable focal muscle twitch within the left first dorsal interosseous muscle. The scalp RMT will be determined using an automatic threshold tracking tool (Awiszus and Borckhardt 2011) as the minimum stimulation intensity needed to elicit a MEP of 50 microvolts in peak-to-peak amplitude in response to 50% of stimuli. EMG signals may be recorded for offline quality control analysis.

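### Experiments 1 and 2 randomise the order of conditions without stating the unit of randomisation; if states are delivered in blocks, within-session drift cannot be separated from state and a random-intercept test understates the error

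*Combined protocol and SAP*

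**What the plan says.** Section 4 (Design and Methodology) lists the brain-state conditions for each experiment: two, with an optional third, in Experiment 1 and three in Experiment 2. Under both lists it states: "The order of conditions will be randomized". Nothing more is said about how the states are sequenced.

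Stimuli are triggered by EEG. For Experiment 1, "The real-time EEG analysis algorithm will trigger delivery of a single TMS pulse when it identifies brain states"; for Experiment 2, Section 11 (Procedure Description) says "TMS will be timed using the real-time EEG analysis algorithm". Each state has its own cap. Section 11 says of Experiment 1: "The real-time EEG algorithm will be used to deliver <= 150 single TMS pulses during brain states associated with strong corticospinal recruitment", with the same cap for the other states, "for a total of <= 450 single TMS pulses". For the triple stimulation technique (TST) in Experiment 2, "<= 50 TST applications will be performed per brain state condition". On spacing, Section 4 requires that "at least 2 seconds will elapse between individual single TMS pulses".

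Section 5 (Data Analysis) plans a linear mixed model for Experiment 1 with "fixed effect of state, random effect of subject". For Experiment 2 it names a fixed effect of state and, specifically, a random intercept for subject. Neither model has a block, order, stimulus-number or by-participant state term. The section does not say whether single stimuli or participant means are analysed.

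**The concern.** Arousal, coil position and electrode contact can change slowly while stimuli are delivered. If all strong-state stimuli come in one run and all weak-state stimuli in another, each participant's strong-minus-weak difference contains whatever changed between the two runs. That part is common to every stimulus in a block, so more stimuli per block do not average it away. A model with only a participant intercept has nowhere to put it and judges the state contrast against stimulus-to-stimulus noise, which is too small a yardstick.

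These comparisons carry Hypotheses 1 and 2. A significant result in either direction could then reflect drift rather than state. If the analysis does allow for the drift, the cost is lost precision in a sample of about 20.

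**Working it through.** **The plan's own figure.** The only planning figure is the target of 20 participants per experiment (Section 14). Section 15 raises it from earlier studies with N = 12 to 17 and gives no effect size, SD or power, so it cannot be reproduced. Solving backwards with a two-sided paired t-test at 0.05, N = 20 gives 80% power at a standardised paired difference of 0.66 and 90% at 0.76.

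**Inputs from the documents.** n = 20; stimuli per state m = 150 (Experiment 1) or 50 (Experiment 2), both upper limits; alpha 0.05. Sidedness is not stated, so two-sided is assumed.

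**Assumed inputs.** Stimulus-level SD 1; each block's mean shifts by an independent amount with SD b, in the same units. The documents give no value for b, so a range is shown.

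**Step 1: false positives with a random intercept only.** With no true effect, a participant's difference between two states has variance 2(1/m + b²) = (2/m)(1 + m·b²). The model assumes 2/m. The variance is therefore understated by the factor 1 + m·b², and

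rejection rate = 2[1 − Φ(1.96 / √(1 + m·b²))].

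| b | 1 + m·b², m = 150 | Rate | 1 + m·b², m = 50 | Rate |
|---|---|---|---|---|
| 0 | 1 | 0.050 | 1 | 0.050 |
| 0.05 | 1.375 | 0.095 | 1.125 | 0.065 |
| 0.1 | 2.5 | 0.215 | 1.5 | 0.110 |
| 0.2 | 7 | 0.459 | 3 | 0.258 |

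Simulation (20,000 null trials per cell) gave 0.095, 0.218 and 0.454 for m = 150, and 0.062, 0.109 and 0.260 for m = 50.

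**Step 2: a different form of drift.** Let the response drift linearly by D SD over the stimulation run. With two blocks in random order the inflation factor is 1 + D²·m/8. For D = 0.3 and m = 150 it is 1 + 0.09 × 18.75 = 2.69, giving a rate of 0.23. Simulated rates (1,000 trials per cell) at D = 0.3 were 0.23 (Experiment 1, two states), 0.31 (Experiment 1, three states) and 0.15 (Experiment 2); at D = 0.5 they were 0.41, 0.58 and 0.29.

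**Step 3: bias.** In these linear-drift simulations the mean estimated state difference stayed within about 0.003 SD of zero. Its spread grew: at D = 0.5, from 0.026 to 0.063 SD (Experiment 1, two states) and from 0.046 to 0.071 SD (Experiment 2).

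**Step 4: remedies.**
- Interleaving stimulus by stimulus: the random-intercept test stayed at about 0.04 to 0.06 for every drift tried (D from 0 to 1).
- Blocks kept, state tested against state-by-participant variation: also about 0.04 to 0.06, with less precision.
- Blocks kept, only a common linear time covariate added: fails when drift differs between people. With participant-specific drift of SD 0.5 the rate was 0.42 (Experiment 1, two states), 0.53 (Experiment 1, three states) and 0.28 (Experiment 2).

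**Step 5: power with a valid participant-level test under blocks.** The loss depends on the assumed true effect.

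| True effect (stimulus SD) | b | m = 150 | m = 50 |
|---|---|---|---|
| 80% power without drift: 0.66·√(2/m) = 0.076 (m = 150), 0.13 (m = 50) | 0.1 | 42% | 63% |
| same | 0.2 | 17% | 36% |
| 0.2 | 0.1 | 99.6% | 93% |
| 0.2 | 0.2 | 79% | 69% |

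**The case against.** The strongest reply is that blocking is inferred. Every stimulus is triggered by the EEG state, which is compatible with interleaving. Where the plan does fix one state per session, in Experiment 3, Section 11 says so; Experiments 1 and 2 have no such sentence. This stands: a reader might infer that the plan prescribes blocks, and it does not. But EEG triggering does not rule blocks out either, since a block aimed at one state is also triggered pulse by pulse. The text randomises the order of conditions and gives each condition its own quota. Experiment 3 uses parallel wording for conditions that each fill a session. Blocks remain the more natural reading.

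Other limits also stand:

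- A reader might infer that drift is systematically counted as a state effect. Random order across participants prevents that on average; the fault is an understated standard error.
- Experiment 1's subject effect is not specified as an intercept and could include a state slope, which would control the error rate. Experiment 2's wording leaves no such room. If participant means are analysed, the false-positive inflation does not arise in either experiment.
- The session limit of 6 hours is not the drift window, because it also covers consent, set-up, thresholding, brain-state discovery and model fitting. At the 2-second minimum, 150 pulses take at least 150 × 2 s = 5 minutes and 450 at least 15. Actual run lengths are not given.
- Interleaving does not deal with genuine differences between people in the state effect. A between-person SD of 0.14 in the state difference (variance 0.02 = 2 × 0.1²) produces the same inflation as b = 0.1, about 21% at m = 150 and 11% at m = 50, even with interleaved stimuli. Only a by-participant state term or participant means covers this.

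**Conclusion.** The point holds conditionally. The unit of randomisation is unstated for Experiments 1 and 2, and no time, block or by-participant state term is specified. If states are blocked and single stimuli are analysed with only a random intercept, assumed block shifts of 0.05, 0.1 and 0.2 SD put the false-positive rate at about 10%, 22% and 46% with 150 stimuli per state, and 6%, 11% and 26% with 50. All of these rest on assumed shifts and on the maximum stimulus counts.

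The documents do not support a claim of biased estimates, nor any single figure for lost power. Large losses appear only when the true effect is assumed to be very small; with an effect of 0.2 SD and a shift of 0.1 SD, power stays at 93% or more.

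This is still more than a missing detail. Interleaving is a better design than randomising the order of blocks, requires no additional stimulation, and cannot be introduced once the data are collected.

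**What to change.** In Section 4, replace the sentence on order for Experiments 1 and 2 with: *The target state for each stimulus is drawn at random in small balanced groups (for example 6 to 12 stimuli), so that strong, weak and, where used, random-state stimuli are interleaved throughout the stimulation run.*

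In Section 5, for both experiments, add a by-participant random state effect (or analyse participant-by-state means) and, in the stimulus-level model, stimulus number as a covariate. State which unit is analysed. The covariate supplements interleaving and the random state effect and replaces neither.

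The cost is slightly more complex trigger code and, where state effects vary between people, a wider but honest standard error. Stimulus and participant numbers do not change. If the team already interleaves, only the wording and the model terms change.

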FORM: IRB Proposal - Standard Submission

NUMBER HRP-UT901 VERSION DATE 8/29/2024

GENERAL STUDY INFORMATION

Use for greater than minimal risk studies and minimal risk studies that fit into one or more expedited categories (see Section 5.3 of our Policies & Procedures for details regarding expedited research).

Do NOT submit this form if the study will qualify for exempt review, instead submit HRP-UT902 IRB Proposal – Exempt Submission Form found in the document Library.

If you are only using secondary data that will not be initially collected solely for this research project, use HRP-UT903 Template IRB Proposal Secondary Use form instead.

For studies following a multi-center or sponsor protocol, please use this guidance to assist in your completion of this form.

For questions regarding definitions, policies, or terms referenced below see the policies and procedures manual.

Please note, Word online does not support Word checkboxes. Please download the file and use your desktop version of Microsoft Word.

1 Review Type (Choose one)

Click on the check box (or double click and type an "X" if using Google Docs) the one review type that applies.

Please note: Expedited Review does not refer to the timeliness of the review of your protocol, but specific categories of research defined by ORHP. If you would like help determining which type of review is most appropriate for your study please contact the Office of Research Support and Compliance: https://research.utexas.edu/ors/about-ors/contact-us/.

a 🖂 Full Board Review – Greater than Minimal Risk Research

b Expedited Review – Minimal Risk Research

2 Research Hypothesis

To input text, click in the light grey area below.

Hypothesis 1 (Experiment 1): Transcranial magnetic stimulation (TMS) can be accurately applied during brain states reflecting strong and weak corticospinal tract recruitment.

Hypothesis 2 (Experiment 2): Transcranial magnetic stimulation (TMS) applied during brain states reflecting strong corticospinal tract recruitment will activate more alpha motoneurons than identical TMS applied during brain states reflecting weak corticospinal tract recruitment or random brain states.

Hypothesis 3 (Experiment 3): Delivering paired corticospinal-motoneuronal stimulation (PCMS) during brain states reflecting strong corticospinal tract recruitment will increase (a) corticospinal transmission, (b) voluntary

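### Experiment 1's only primary test is a state effect that may include an optional random condition, not the strong-versus-weak contrast that Hypothesis 1 concerns

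*Combined protocol and SAP*

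**What the plan says.** Section 2 states Hypothesis 1 for two states: TMS "can be accurately applied during brain states reflecting strong and weak corticospinal tract recruitment". The first aim in section 3 is to validate the accuracy of real-time state-dependent TMS.

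Section 4, Experiment 1, lists strong and weak as conditions without qualification and then adds: "TMS may also be applied during random brain states". The real-time paragraphs of section 4 and the Experiment 1 steps in section 11 also treat random as optional. Section 4 describes the random option as a mixed draw from the strong and weak states.

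Section 5, Experiment 1, gives the only primary outcome as "Amplitude of MEPs evoked during brain states reflecting strong, weak, and/or random corticospinal tract recruitment". The analysis is by "linear-mixed effects models (fixed effect of state, random effect of subject) with alpha equal to 0.05". It names no muscle, contrast, sidedness or rule for choosing between a two-level and a three-level state factor.

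The same section is tighter elsewhere. The Experiment 2 primary outcome is "amplitude of FDI muscle response after TST application during brain states reflecting strong, weak, and random corticospinal tract recruitment", which fixes both muscle and states. The Experiment 3 primary outcomes also name FDI, and correction of post-hoc contrasts is stated there only.

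On muscles, the Experiment 1 EMG paragraph in section 4 says "EMG will be recorded from a maximum of 5 hand and wrist muscles while participants rest quietly and during stimulation procedures" and then "EMG will be recorded from <= 8 hand and wrist muscles". Section 11 gives 5. Left FDI appears in the Experiment 1 procedures as the muscle that defines the TMS hotspot.

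**The concern.** Which hypothesis the primary test addresses depends on an operational decision. If only strong and weak pulses are delivered, the state effect has 1 degree of freedom and is the strong-weak comparison. If random pulses are added, the same model line yields a 2-degree-of-freedom test of any difference among three states, and its p-value no longer answers the strong-weak question alone.

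This has two consequences. First, when random lies between strong and weak, the extra degree of freedom adds little signal and power for the question of interest falls. Second, because the plan does not say which test decides, a team holding all three conditions could report either one at 0.05. Experiment 1 is the study's validation step, so its one primary test should be fixed before data are seen.

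**Working it through.** **The plan's own figures.** Section 14 sets a target of 20 participants. This cannot be reproduced: section 15 argues from earlier studies of 12 and 17 participants and gives no effect size, SD, power figure or contrast. Alpha of 0.05 is the true error rate only if one test is fixed in advance.

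**Inputs.** From the documents: N = 20 (section 14), alpha 0.05 (section 5), and random as a mix of strong and weak (section 4). Assumed: a two-sided test; a standardised paired strong-weak difference d of 0.66 or 0.5; random at the midpoint; equal variances and correlations across states. Tests on participant-by-state means stand in for the mixed model.

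**Strong minus weak, 1 df.** Paired t test, 19 df, critical value 2.093, noncentrality d√N.
- d = 0.66: 0.66 × √20 = 2.95; power 80%.
- d = 0.5: 0.5 × √20 = 2.24; power 56%.

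**Three-level state effect, 2 df.** Let the means be −δ/2, 0 and δ/2, so the squared deviations sum to δ²/2. With within-participant error variance σ², the paired-difference SD is √2·σ, so δ²/σ² = 2d². The noncentrality is λ = N × (δ²/2)/σ² = N·d². The reference distribution is F(2, 38), with critical value 3.245.
- d = 0.66: λ = 20 × 0.4356 = 8.71; power 72%.
- d = 0.5: λ = 20 × 0.25 = 5.00; power 47%.

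| Assumed d | Strong minus weak | Three-level test, random midway | Loss |
|---|---|---|---|
| 0.66 | 80% | 72% | 8 points |
| 0.5 | 56% | 47% | 9 points |

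The loss depends on where random falls. It shrinks, and can reverse, as random moves from the midpoint towards one of the targeted states. Any such gain comes from the random comparison.

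**Choice between the two tests.** No state differences, one muscle, N = 20, each test at 0.05. The chance that at least one of the strong-weak test and the three-level test is significant was 0.079 in 20,000 simulated trials and 0.075 in a repeat with 200,000. Each test alone stayed near 0.05. The two tests overlap heavily, so the excess is moderate.

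**After the fix.** With one muscle and one contrast, type I error is 0.05. At N = 20, power is 80% at d of about 0.66 and 90% at about 0.76.

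**The case against.** The best reply is that the intent is clear. Left FDI is the hotspot muscle, strong and weak are listed as unqualified conditions, and Hypothesis 1 names those two states. A team following that intent would test FDI, strong against weak, at a true 0.05. This is a fair account of the likely intent and it makes the muscle gap mostly missing detail. But it does not bind the analysis: section 5 still tests the state factor as a whole, with random in or out.

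Several stronger readings are tempting, and the objection is right to resist them:

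- A reader might infer that random pulses alone could make the test positive while strong equals weak. Section 4 describes random as a mix of the two states. If they do not differ, a mix of them should not differ from either, and the plan suggests no other mechanism.
- A reader might infer a large error inflation across 5 or 8 recorded muscles. That requires testing each muscle separately and reporting the best, which the plan does not propose.
- A reader might count three uncorrected pairwise state comparisons. Section 5 lists none for Experiment 1.
- A reader might infer that Experiments 2 and 3 depend on this p-value. No text makes them conditional on it, and each repeats brain state discovery and has its own check of targeting accuracy.

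The objection also notes that Hypothesis 1 is about accurate delivery, whereas the outcome is MEP amplitude. That is a separate gap: naming the contrast does not explain how an MEP difference demonstrates accuracy.

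**Conclusion.** The concern holds in a limited form. When the optional random condition is run, Experiment 1's only primary test does not isolate the strong-weak comparison, and the plan does not say which test decides. The cost is about 8 to 9 percentage points of power under the midpoint assumption, and a type I error of about 0.08 in place of 0.05 if the choice of test is left until the data are seen. Both are moderate.

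The power figures rest on assumed effects of 0.66 and 0.5 and on the midpoint placement. The error figure needs no effect size but assumes that either test could be reported; it is not a prediction of what the team will do. If random is never run and FDI is analysed, neither cost arises. The documents do not support a claim that the primary result is likely to be a false positive from another muscle or from the random condition. The change is worth making because it costs almost nothing.

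**What to change.** In section 5, Experiment 1:

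1. State the primary outcome as left FDI MEP amplitude.
2. State the deciding test as the strong-minus-weak contrast from the mixed model, 1 degree of freedom, two-sided alpha 0.05.
3. Replace the and/or wording, here and in sections 4 and 11, so that every participant receives both strong and weak states and only random is optional.
4. Label random-state comparisons and MEPs from other muscles as secondary, with no bearing on Hypothesis 1.
5. Add a sentence saying how the MEP contrast bears on targeting accuracy.

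As tidying, reconcile the 5- and 8-muscle limits in the Experiment 1 EMG paragraph of section 4.

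The cost is wording only: no extra pulses, sessions or participants. The small downside is that random-state and non-FDI results can no longer be used to support Hypothesis 1.
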